### 2.2.2 Secondary endpoints

- Distribution of age, gender, smoking habits, professional status, family history, educational level, subject income by IBD type.
- Distribution of clinical variables (steroid behaviour, anthropometric information, medical history and comorbidities, clinical characterization of disease) by BD type.
- Therapies for IBD (aminosalicylates, steroids, immunomodulators, immunosupressors biologics, antibiotics, probiotics and surgeries) and the length of these therapies during the previous 3 years. Property of Taked

Proportion of biologic-experienced patients.

Proportion of patients who have not responded previously to biologic therapies and reason.

- IBD treatment introduced at Day 1 (if applicable).
- Socio-demographic, clinical and treatment-related variables in patients with moderate to severe activity of CD (HBI score  $\geq$  8 or CDAI score  $\geq$  220 points) versus patients with mild or no activity (HBI score < 8 or CDAI score < 220 points).

- Socio-demographic, clinical and treatment-related variables in patients with moderate to severe activity of UC (9-point partial Mayo score ≥5) versus patients with mild or no activity (9-point partial Mayo score <5).
- Mean score of EQ-5D by IBD type.
- Mean score of different components of SF-36 by IBD type.
- Mean total score of IBDQ and by domain (bowel symptoms, systemic symptoms, emotional function and social function). Patients with ostomy will a in the applicable not be evaluated since this questionnaire is not validated to be used in this population.
- Mean total percentage of work impairment (WPAI).
- Mean work time missed (WPAI).
- Mean impairment while working (WPAI).
- Mean total activity impairment (WPAI).
- Healthcare resources (previous 3 years): drug therapies, imaging and laboratory testing, surgeries, hospitalizations and consultations. y and sul

### STUDY DESIGN 3

This is a multicenter, non-interventional, cross-sectional study (Figure 1) aiming primarily to determine the rate of control of IBD activity (Crohn's Disease [CD] or Ulcerative Colitis [UC]). At each center, eligible subjects will be identified consecutively as they attend a scheduled clinical appointment with their physician (Day 1). Upon written consent, data regarding disease activity, treatment patterns, burden of disease and quality of life will be collected from the patients' medical records and administered Patient Report Outcome (PRO) questionnaires, including quality of life (SF-36, EQ-5D and IBDQ) and work productivity (WPAI) questionnaires. Besides the cross-sectional data collection, the study will have an additional retrospective data collection referring to the three years previous to Day 1, regarding the previous IBD treatments (drug, dose, treatment duration and drug changes), and use of other healthcare resources related with the management of IBD. Property of

Day 1

### **Exclusion Criteria** 4.2

Property of

Subjects will be excluded if presenting at least one of the following:

- 1. Indeterminate or not classified colitis.
- 2. Current or previous participation in interventional clinical trials (within the last 3 years).
- 3. Presenting mental incapacity, unwillingness or language barriers precluding adequate understanding or cooperation.

### 5 PROTOCOL CLARIFICATIONS

The last secondary objective, estimation of healthcare resources cost, will not be calculated as stayed in section 3 of the protocol (3. Study objectives), since these variables were not The of Use collected in the CRF.

Adverse events were not collected in the study database and results regarding these variables will not be presented in the statistical report.

Secondary endpoint "Proportion of patients who guit their job due to IBD and have not been able to return to work" will not be calculated as stayed in section 10.1.1 of the protocol (10.1.1 Study endpoints), since these variables were not collected in the CRF

In the protocol the analysis dataset was not defined. In this SAP the analysis dataset was defined according to section 6 Definition of analysis subsets.

The descriptive analysis for continuous variables will be summarized by mean, standard variation, median, maximum, minimum as stayed in the protocol and also by first quartile and third quartile.

## 6

DEFINITION OF ANALYSIS SUBSETS only and Analysis dataset - All patients fulfilling selection criteria (section 4), who provided the written informed consent, without major study protocol deviations and who have completed the Day 1 assessment will be included in the statistical analysis dataset.

### RATIONALE AND CALCULATION OF THE SAMPLE SIZE 7

It is expected to include 246 patients regardless of IBD type.

This sample size will allow estimates with 95% confidence interval and a margin of error less than 5%, and assuming a rate of inadequate control of disease of 20% (conservative approach), regardless of IBD type. The following formula was used:

$$n = \frac{1.96^2 \times p \times (1-p)}{ME^2}$$

Rate of uncontrolled disease (p) = 20%

Margin of error (ME) = 0.05

Expected recruitment period: 6 months

ofUse

## 8 STATISTICAL METHODS

For each study endpoint, data will be summarized for total IBD patients and by IBD type (CD and UC).

Statistical analysis will allow a characterization of the study population, the estimation of primary endpoints and to compare the subgroup of patients with mild or no activity of disease and those with moderate to severe activity. A descriptive analysis will be obtained for all relevant variables, with absolute and relative frequency for categorical variables and mean, standard variation, median, maximum, minimum, first quartile and third quartile, for continuous ones. For each study endpoint, data will be summarized by IBD type (CD or UC). Hence, for each IBD type, the patients with disease activity will be compared with patients with mild or no activity regarding socio-demographic, clinical and treatment variables of interest. The variable normality assumption will be tested using the Kolmogorov-Smirnov test or Shapiro-Wilk test as applicable. Non-parametric tests will be used whenever the assumptions for parametric tests are not accepted. Chi-square or Fisher exact tests will be used to compare activity vs non-activity regarding qualitative variables and t-student / Mann-Whitney tests will be used for comparison of quantitative variables. If applicable, logistic regression will be used for evaluating associated variables. Variables with clinical significance or statistical significance (p<0.200) will be included in the initial logistic regression model, or otherwise specified by the sponsor. All tests will be two-sided considering a significance level of 5%.

Data analysis will be performed using SAS® (version 9.4; SAS Institute Inc, Cary, USA).

There will be no imputation of missing data for this study, unless otherwise specified.

In case of complete missing dates, date is to be considered as missing.

In case of partial dates:

Missing day is to be considered as the 15th day of the month;

• Missing day and month are to be considered as the 1st day of July.

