- The SF-36 uses 36 items to evaluate eight health dimensions (Physical functioning, Role Physical, Body pain, General health, Vitality, Social Functioning, Role-Emotional, Mental Health) and based on standardized scores, two summary scores are to be estimated (Physical Component Score and Mental Component Score). The standard scoring method for SF-36 questionnaire will be obtained using the QualityMetric Health Outcomes™ Scoring Software 4.5 provided by QualityMetric Incorporated.
- The IBDQ score and each of the four IBDQ domains (Bowel systems, Emotional health, Systematic systems and Social function). Total IBDQ score range from 32 to 224, with a higher score reflecting better quality of life. Response to each of the questions is graded from 1 to 7 ("1" being the worst situation and "7" the best). Please see section 9. *Data, derivations and transformations* for the IBDQ scores calculation. Note: The IBDQ is not validated for patients with ostomies and therefore should not be applied for these patients.
- The comparison of SF 36 scale scores or component summary scores, EQ-5D VAS scale and IBDQ domain scores or total score according to disease activity will be performed through the t-test for independent samples or Mann-Whitney test in case of non-normality of the quantitative variable distribution. The association between each EQ-5D dimension and disease activity will be determined for each IBD type using Chi-Square Test.

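### Comparisons of active with non-active patients name no unequal-variance t-test, so the 5% level can drift either way if spreads differ in unequal groups

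*SAP*

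**What the plan says.** SAP 8 compares groups within disease type: "for each IBD type, the patients with disease activity will be compared with patients with mild or no activity". For numerical variables, "t-student / Mann-Whitney tests will be used for comparison of quantitative variables". The choice follows a pretest: "The variable normality assumption will be tested using the Kolmogorov-Smirnov test or Shapiro-Wilk test as applicable". A general clause sends variables to non-parametric tests when parametric assumptions are not accepted, without listing those assumptions.

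SAP 8.2 is narrower for SF-36, EQ-5D VAS, IBDQ and WPAI: "t-test for independent samples or Mann-Whitney test in case of non-normality of the quantitative variable distribution". Protocol 10.3 has the same rule. Tests are two-sided at 5%. No equal-variance check and no Welch or Satterthwaite test is named.

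On size, SAP 7 says "It is expected to include 246 patients regardless of IBD type", based on a 20% rate of uncontrolled disease and "Margin of error (ME) = 0.05". Neither document plans group sizes by activity or a CD/UC split, and neither gives an SD. The SAP specifies confidence intervals for the primary proportions and the odds ratios, but not for differences in means.

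**The concern.** The Student t-test pools the two variances. With equal group sizes that does little harm when spreads differ. With unequal sizes the pooled estimate is dominated by the larger group. If the smaller group is the more variable, the standard error is too small and the test rejects too often. If it is the less variable, the test rejects too rarely. A normality pretest does not detect this, because two normal samples with different SDs both pass.

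The comparison by activity is a named secondary objective and covers quality of life, work productivity, age, time since diagnosis and treatment duration. SAP 8 also admits variables to the logistic model at p<0.200. If those p-values come from the same tests, the choice of variables is affected too.

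**Working it through.** **Plan's own figure.** n = 1.96² × 0.20 × 0.80 / 0.05² = 245.86, rounded up to 246. This agrees with SAP 7 and protocol 10.6.

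**Group sizes.** Assuming an even CD/UC split, 246 / 2 = 123 per type. Active: 0.20 × 123 = 24.6, taken as 25. Non-active: 123 − 25 = 98.

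**Large-sample level of the pooled t-test, equal means.** Let r be SD(active)/SD(non-active), with the non-active SD set to 1.

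- Variance the test uses: Vp = [(24r² + 97)/121] × (1/25 + 1/98)
- True variance: Vt = r²/25 + 1/98
- Actual level = 2 × [1 − Φ(1.96 × √(Vp/Vt))]

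For r = 1.5: Vp = (151/121) × 0.050204 = 0.06265; Vt = 0.09 + 0.010204 = 0.10020; √(Vp/Vt) = 0.791; level = 12.1%.

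For r = 2: Vp = (193/121) × 0.050204 = 0.08008; Vt = 0.17020; √(Vp/Vt) = 0.686; level = 17.9%.

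For r = 0.67: Vp = (107.77/121) × 0.050204 = 0.04472; Vt = 0.02816; √(Vp/Vt) = 1.260; level = 1.35%.

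**Simulation, 25 vs 98, normal data, equal means** (8,000 runs for ratios 0.67, 1.5 and 2). The planned rule was taken as Shapiro-Wilk in each group at 5%, then Student or Mann-Whitney.

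| SD ratio | Student | Mann-Whitney | Planned rule | Welch |
|---|---|---|---|---|
| 0.67 | 1.3% | 2.4% | 1.5% | 5.1% |
| 1.5 | 12.1% | 8.6% | 12.0% | 5.4% |
| 2 | 18.2% | 10.8% | 17.8% | 5.1% |

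At ratio 1 all four gave 4.7–5.7%. A separate simulation with 4,000 runs of the planned rule gave 1.8%, 5.1%, 11.3% and 15.9% at ratios 0.67, 1, 1.5 and 2, which is the same pattern.

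**Sensitivity to the CD/UC split.** The protocol's Introduction cites a local UC:CD ratio of 7.04:1. Applied to 246 this gives 246/8.04, about 31 CD patients, or 6 active vs 25. At SD ratio 1.5: Student 12.8%, planned rule 12.6%, Welch 5.6%.

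**Sensitivity to the active share.** Student t-test, large-sample formula, 123 patients, SD ratio from 0.5 to 2:

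| Active share | Level at ratio 0.5 | Level at ratio 2 |
|---|---|---|
| 20% | 0.4% | 17.9% |
| 30% | 1.2% | 12.6% |
| 40% | 2.7% | 8.3% |
| 50% | 5.1% | 4.9% |

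**Does Welch work everywhere?** No. With identical skewed distributions in both groups (a true null; shapes assumed):

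- Lognormal, 25 vs 98: Welch about 7.4%.
- 80% zeros: Welch about 8.3% at 25 vs 98 and 15.4% at 6 vs 25.
- The planned rule gave 3.4–4.6% in these cases.

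**Combined rule.** Welch where the plan would use Student, with Mann-Whitney kept otherwise, gave 5.1–6.0% on normal data at SD ratios 0.67 to 2. It also held its level in the skewed cases.

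**The case against.** Five points can be made in the plan's defence.

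- **The 1:4 ratio.** A reader might take it as a fact of the study. It is only the 20% planning rate, stated without regard to IBD type. Protocol 6.2 expects active patients to be over-represented because they attend more often, so the groups may be less unequal. This stands.
- **Unequal spread.** A reader might infer it from the bounded questionnaire scales. Bounds make it plausible but do not establish it, and they do not apply to age or time since diagnosis. A group sits nearer a bound only if the groups differ in location, and then rejection is not a false positive. The harm in that case is a misstated p-value or misjudged power. This stands too, so the error rates above apply to equal means with unequal SDs.
- **The general clause on parametric assumptions.** It could be read to include equal variance. Adding a 5% variance F-test that leads to Mann-Whitney (normal data, no normality step) gave 8.9% at ratio 1.5 and 11.1% at ratio 2. That is lower, but not 5%.
- **What may already be covered.** SAP 8.2 does not say its t-test is pooled, the planned SAS t-test procedure reports the Satterthwaite result anyway, and the protocol summary allows 95% intervals where relevant. The table shells are a separate document not available here. All this makes the change easy, but the SAP still does not say which result is to be read.
- **Descriptive purpose.** Protocol 10.5 calls all analyses descriptive, which limits the weight of the point.

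**Conclusion.** The point holds in conditional form. If SDs differ and the groups are as unequal as the planning rate implies, the nominal 5% level can be wrong in either direction: about 1.5% at SD ratio 0.67, 12% at 1.5 and 18% at 2. This rests on assumed SD ratios, an even CD/UC split, 20% active and equal means on normal data. With equal spread every procedure stays near 5%, and near 50% active the distortion of the t-test disappears.

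Two stronger conclusions are not supported. The documents do not show that every quantitative comparison has the wrong error rate. Nor does the calculation support Welch for all variables, since it is too liberal for skewed or zero-heavy data in small unequal groups. The primary proportions, their intervals and the sample size of 246 are untouched.

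**What to change.** In SAP 8 and 8.2, and for consistency protocol 10.3, state that wherever a t-test is used it is the Welch (Satterthwaite) version, reported with the mean difference and its 95% CI. Keep Mann-Whitney for clearly skewed or zero-heavy variables, such as WPAI absenteeism, treatment durations and counts. Because Mann-Whitney also moves off 5% when spreads differ, describe its result as a comparison of distributions, not of means.

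The cost is a sentence or two in the SAP. No new data or change in sample size is needed, and the planned software already produces the result. The downside is a negligible loss of power when spreads are equal.

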#### **Study Schedule** 6.1

Planned Start of Study:

Planned collection of first data point:

Planned End of Study:

Planned completion of the Study Report:

The Start of Study is defined as date of last protocol signature and planned to occur on the 1st quarter 2018. The collection of first data point (first patient in) will start during 1st quarter 2018. The recruitment period is expected to last up to 6 months. The End-of-Study is defined as the date of collection of the last data point for the last patient recruited.

CRO (on behalf of the Sponsor) will ensure that End-of-Study notification is submitted to the concerned authorities and IEC for each site, for the country and for the complete study, as locally required.

Based on upcoming knowledge, Takeda might choose to terminate the study prematurely. In such case, the Committee(s), study sites, IECs and authorities will be informed promptly.

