# 10.5 Handling of missing data

Given that all analyses are descriptive in nature, no imputation of missing data will be performed, except when detailed in the SAP regarding the PRO tools.

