is of Use

**Total number of hospitalizations per patient** – Sum of all previous hospitalizations due to IBD for each patient in the previous 3 years.

**Time of hospitalization** – The difference between the start date and end date of each hospitalization, in days. For each patient all hospitalized time will be summed. Time of hospitalization will only be calculated if start date and end date of hospitalization is complete.

**Total number of medical appointments per patient –** Sum of all previous medical appointments for IBD by each patient in the previous 3 years.

Any change in IBD treatment during medical appointments in the previous 3 years per patient – A dichotomous variable (yes/no) will be calculated:

Yes – Patients with at least one medical decision regarding any IBD classes classified as: Introduced a new therapeutic class, Discontinuation (no switch), Drug change (same therapeutic class) or Switched of therapeutic class or Dose changed (same drug).

No – Patients without medical decisions regarding any IBD classes classified as: Introduced a new therapeutic class, Discontinuation (no switch), Drug change (same therapeutic class), Switched of therapeutic class or Dose changed (same drug).

Total number of IBD treatment changes per patient during medical appointments in the previous 3 years – Sum of all medical decisions classified as Introduced a new therapeutic class, Discontinuation (no switch), Drug change (same therapeutic class), Switched of therapeutic class or Dose changed (same drug) for all medical appointments and any IBD classes, in the previous 3 years, for each patient.

**Height (in the previous 3 years, not considering Day 1)** – For each patient, height in the previous 3 years will be calculated by the mean of all heights collected in that period.

Weight (in the previous 3 years, not considering Day 1) – For each patient, weight in the previous 3 years will be calculated by the mean of all weight collected in that period.

IBM (in the previous 3 years, not considering Day 1) - The following formula must be i erms of Use considered:

*IBM* (*in the previous* 3 *years*)

Mean weight in the previous 3 years not considering Day 1 (Kg) Mean height in the previous 3 years , not considering Day 1  $(m)^2$ 

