Yes – Patients with at least one IBD treatment (just IBD class of salicylic derivates, corticosteroids, immunosuppressors or biologic therapy) with end date equal to Day 1 date and reason for end of IBD treatment classified as "Dose changed".

No – Patients without any IBD treatment (just IBD class of salicylic derivates, corticosteroids, immunosuppressors or biologic therapy) with end date equal to Day 1 date and reason for end of IBD treatment classified as "Dose changed".

Total number of IBD treatments during retrospective period (previous 3 years and at Day 1) per patient – Sum of IBD treatments reported during retrospective period (3 years) for each patient in the previous 3 years and including IBD treatment starting at Day 1.

**IBD treatment duration** – Time between the beginning of the IBD treatment until the end of the treatment (in months). For patients with ongoing IBD treatment at Day 1, stop date will be considered as Day 1 date visit.

**Salicylic derivates treatment duration per patient** – Sum of all IBD salicylic derivate treatments duration for each patient (in months). If the patient has two IBD salicylic derivate treatments taking in simultaneous, it will only be considered the treatment with the longest duration.

**Corticosteroids treatment duration per patient** – Sum of all IBD corticosteroid treatments duration for each patient (in months). If the patient has two IBD corticosteroids treatments taking in simultaneous, it will only be considered the treatment with the longest duration.

IS OF USE

Immunosuppressors treatment duration per patient - Sum of all IBD immunosuppressor treatments duration for each patient (in months). If the patient has two IBD immunosuppressors treatments taking in simultaneous, it will only be considered the treatment with the longest duration.

Biologic therapy treatment duration per patient - Sum of all IBD biologic therapy treatments duration for each patient (in months). If the patient has two IBD biologic therapies taking in simultaneous, it will only be considered the treatment with the longest duration

Antibiotics treatment duration per patient - Sum of all IBD antibiotic treatments duration for each patient (in months). ,ct to

Nutritional support treatment duration per patient - Sum of all IBD nutritional support snd treatments duration for each patient (in months).

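### The SAP's partial-date rule is not tied to Day 1 or to the paired date, so it can give negative or zero treatment durations, and it departs from protocol 10.5 without saying so

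*SAP*

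**What the plan says.** SAP section 8 starts from a general position: "There will be no imputation of missing data for this study, unless otherwise specified". It then gives three date rules.

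- Wholly missing date: "In case of complete missing dates, date is to be considered as missing".
- Day missing: "Missing day is to be considered as the 15" (that is, the 15th of the recorded month).
- Day and month missing: "Missing day and month are to be considered as the" first of July of the recorded year.

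No rule relates the imputed date to Day 1 or to the other date of the same course.

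SAP section 9 defines treatment duration as stop minus start, in months, and adds durations per patient within each drug class. Day 1 enters in one place only: "For patients with ongoing IBD treatment at Day 1, stop date will be considered as Day 1 date visit". That fixes the stop date of an ongoing course and leaves an imputed start free to fall later. Nothing is said about negative or zero results. For time in hospital the same section is stricter: it "will only be calculated if start date and end date of hospitalization is complete".

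Length of therapies over the previous three years is a secondary endpoint (SAP 2.2.2), and duration of treatment is compared by disease activity (SAP 8.2).

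Protocol 10.5 says that "no imputation of missing data will be performed, except when detailed in the SAP regarding the PRO tools". SAP section 5, which lists clarifications to the protocol down to the addition of quartiles, does not mention dates.

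**The concern.** Start and stop dates taken retrospectively from charts are where partial dates are to be expected. A fixed day is a reasonable default when the two dates of a course are far apart. It fails when they lie in the same month or year, or when the partial date lies in the month or year of Day 1. A start can then land after its own stop, or both dates can land on the same day. The resulting value is impossible or uninformative, yet the plan as written keeps it and adds it to the patient's other courses.

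At stake are the tabulated minima and quartiles of treatment length, the per-class sums for individual patients, and the Mann-Whitney comparisons by activity. There is also a question of transparency: a reader of protocol 10.5 would not expect dates to be imputed at all.

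**Working it through.** The plan gives no figure for partial dates or durations, so there is none to reproduce. The check applies the SAP section 8 rule to the SAP section 9 definition, duration = stop - start, with one month = 30.4375 days.

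**Worked cases** (true dates are illustrative)

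| Recorded | True days | SAP days |
|---|---|---|
| Start 'March 2018' (true 2 March), ongoing, Day 1 10 March 2018 | 8 | 10 March - 15 March = -5 |
| Start '2018' (true 10 January), ongoing, Day 1 20 March 2018 | 69 | 20 March - 1 July = -103 |
| Start '2017' (true 20 January), stop 20 April 2017 | 90 | 20 April - 1 July = -72 |
| Start 1 September 2017, stop '2017' (true 20 December) | 110 | 1 July - 1 September = -62 |
| Both 'May 2017' (true 2 to 28 May) | 26 | 15 May - 15 May = 0 |
| Both '2017' (true 1 February to 1 November) | 273 | 1 July - 1 July = 0 |

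With one partial date the most negative value is -16 days (day missing) or -183 days (day and month missing). The year is illustrative. The protocol plans first data for the first quarter of 2018 and states "The recruitment period is expected to last up to 6 months", but any year-only date in the year of the visit falls after Day 1 if the visit is before 1 July.

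**Effect on a class sum.** A complete course from 1 April to 1 December 2017 lasts 244 days (8.02 months). Add the second case above: (244 - 103)/30.4375 = 4.63 months, against a true (244 + 69)/30.4375 = 10.28 months.

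**Frequency under assumptions.** The documents do not give the share of partial dates, so it was varied. Other assumptions: Day 1 from mid-January to mid-July 2018, starts uniform over the previous three years, exponential lengths, and partial dates unrelated to length; 60,000 courses per scenario.

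| Mean of length distribution (months) | Day missing / day and month missing | Negative | Zero | Mean duration, true vs SAP (months) |
|---|---|---|---|---|
| 2 | 20% / 5% | 4.9% | 1.3% | 1.88 vs 1.88 |
| 2 | 30% / 20% | 13.2% | 5.5% | 1.87 vs 1.85 |
| 2 | 20% / 50% | 19.0% | 20.8% | 1.87 vs 1.88 |
| 6 | 20% / 5% | 2.6% | 0.6% | 4.97 vs 4.98 |
| 6 | 30% / 20% | 7.4% | 2.8% | 5.00 vs 5.02 |
| 6 | 20% / 50% | 12.2% | 13.3% | 4.98 vs 4.98 |
| 18 | 20% / 5% | 1.3% | 0.2% | 10.20 vs 10.20 |
| 18 | 30% / 20% | 4.0% | 1.3% | 10.16 vs 10.16 |
| 18 | 20% / 50% | 7.3% | 6.2% | 10.23 vs 10.25 |

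Over- and underestimates cancel across records, so the mean barely moves. They need not cancel within a patient.

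**Would a cap be enough?** Capping imputed dates at Day 1 and at the paired date removes every negative but turns it into a zero. In the scenario with mean 6 and 30% / 20%, negatives go from 7.4% to 0% and zeros from 2.8% to 10.2%. Zeros come from coinciding dates and need their own rule.

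**Which other intervals are exposed?** Time since first treatment and time from diagnosis to initial treatment carry the same risk. Time since moderate-to-severe diagnosis does not go negative, because inclusion criterion 3 requires at least six months. Taking six months as 184 days, the smallest value under the 1 July rule is 3 days (diagnosis 1 January, Day 1 4 July). It can therefore be understated, but not reversed.

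**The case against.** Several points on the other side are sound.

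- The number of affected records is unknown and may be small. Protocol 6.2 expects records for the three years to be largely complete, and the data validation plan in protocol 9.4.1 provides for queries on missing and inconsistent data. Queries can reduce partial dates, but they do not repair the ones that remain and are imputed. The table shells are an external document and might hold a further rule.
- A reader might infer that mean treatment lengths are biased. The table above does not support that. Large effects on the mean appear only among courses that start and end in one calendar year, and their size depends on the model. For a year-only start with a known stop, if the stop is uniform over the year, half are negative and the mean is 0 months against a true 3. If start and stop are two ordered uniform dates, a quarter are negative and the mean is 2 against 4.
- A reader might call the rule a plain contradiction of the protocol. That goes too far. Protocol section 10 allows a revised SAP to describe deviations with their reason, and SAP section 8 leaves room for specified exceptions. What is missing is the declaration and the reason.
- A reader might extend the problem to the main result. The primary endpoint uses Day 1 scores, and hospital time requires complete dates, so neither is touched.
- A false started-at-Day-1 flag needs a partial start whose imputed date happens to be the visit date. This is possible but should be rare, since treatments begun at Day 1 are recorded at that visit.

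None of this supplies an ordering rule or a way to handle impossible values.

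**Conclusion.** The concern holds for secondary, mainly descriptive results. Followed as written, the rule can yield negative durations because nothing ties an imputed date to Day 1 or to its pair. It can yield zero durations because two partial dates in the same month or year receive the same day. Both feed the per-class sums behind a secondary endpoint and its comparison by activity. That they can occur follows from the wording alone. Their frequency does not: the 1.3% to 19.0% negative and 0.2% to 20.8% zero are results of assumed shares and lengths. The damage falls on individual values, extremes, quartiles, patient sums and rank tests. The date imputation is also an undeclared departure from protocol 10.5. It should be corrected before analysis because the correction is cheap.

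**What to change.** In SAP section 8:

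1. Keep the 15th and 1 July as defaults unless the imputed date falls after Day 1, or is out of order or coincident with its paired date.
2. In those cases, use a date within the part of the recorded month or year, from its first to its last day, that is also on or before Day 1 and in order with the pair. The midpoint is a natural choice. For start '2018' and Day 1 20 March 2018, the feasible span is 1 January to 20 March (78 days), and the midpoint gives 39 days in place of -103. The end of the recorded period must be one of the limits: without it, a start '2016' ongoing at 1 April 2018 would be placed on 14 February 2017, outside its own year.
3. If both dates are partial in the same period, place them in order within it or set the duration to missing.
4. Do not let imputed dates trigger the flags that require equality with the Day 1 date.

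In SAP section 5, declare the date imputation with its reason. In the report, give the number of imputed dates by variable and add a sensitivity analysis limited to complete dates, the standard that SAP section 9 already sets for hospital time.

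The cost is a few lines of SAP text and a short programming rule, with no new data. There is a trade-off. When every partial date was placed at the midpoint of a properly bounded interval (mean length 6 months, 30% / 20% partial), mean absolute error per record fell from 1.14 to about 0.9 months, but the mean rose from a true 4.96 to 5.39 months. Keeping the defaults wherever they work changes fewer records. Some upward shift should still be expected if many dates are year-only, and the complete-date analysis will show it.
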